10.4.2 Contraception Guidance

For Women of Childbearing Potential

Agreement to remain as abstinent (refrain from heterosexual intercourse) or use contraceptive methods that result in a failure rate of <1% per year during the treatment period and for at least 90 days after the last dose of study intervention.

- a. A woman is considered of childbearing potential if she is postmenarchal, has not reached a postmenopausal state (≥12 months of amenorrhea with no identified cause other than menopause), and has not undergone surgical sterilization (removal of ovaries and/or uterus). The definition of childbearing potential may be adapted for alignment with local guidelines or requirements.
- b. Examples of contraceptive methods with a failure rate of <1% per year include bilateral tubal ligation, male sterilization, established, proper use of hormonal contraceptives that inhibit ovulation, hormone-releasing intrauterine devices, and copper intrauterine devices.
- c. Contraception methods that do not result in a failure rate of <1% per year such as cap, diaphragm, or sponge with spermicide, or male or female condom with or without spermicide, are not acceptable.

The reliability of sexual abstinence should be evaluated in relation to the duration of the clinical trial and the preferred and usual lifestyle of the subject. Periodic abstinence (e.g., calendar, ovulation, symptothermal, or post-ovulation methods) and withdrawal are not acceptable methods of contraception.

For Men:

Agreement to remain abstinent or use contraceptive measures and agreement to refrain from donating sperm, as defined below:

a. With female partners of childbearing potential, men must remain abstinent or use a condom plus an additional contraceptive method that together result in a failure rate of <1% per year during the treatment period and for at least 30 days plus 90 days (a spermatogenesis cycle) after the last dose of study intervention. Men must refrain from donating sperm during this same time period

10.4.3 Collection of Pregnancy Information

Female Subjects Who Become Pregnant

- The Investigator will collect pregnancy information on any female subject who becomes pregnant while participating in this study. The initial information will be recorded on the appropriate form and submitted to the Sponsor within 24 hours of learning of a subject's pregnancy.
- The subject will be followed to determine the outcome of the pregnancy. The Investigator will collect follow-up information on the subject and the neonate and the information will be forwarded to the Sponsor. Generally, follow-up will not be required for longer than 6 to 8 weeks beyond the estimated delivery date. Any termination of pregnancy will be reported, regardless of fetal status (presence or absence of anomalies) or indication for the procedure.
- While pregnancy itself is not considered to be an AE or SAE, any pregnancy complication or elective termination of a pregnancy for medical reasons will be reported as an AE or SAE.
- A spontaneous abortion (occurring at <22 weeks gestational age) or stillbirth (occurring at >22 weeks gestational age) is always considered to be an SAE and will be reported as such.
- Any post-study pregnancy related SAE considered reasonably related to the study intervention by the Investigator will be reported to the Sponsor, as described in Section 8.3.5.
 While the Investigator is not obligated to actively seek this information in former study subjects, he or she may learn of an SAE through spontaneous reporting.
- Any female subject who becomes pregnant while participating in the study will discontinue study intervention or be withdrawn from the study.

Male Subjects with Partners Who Become Pregnant

• The Investigator will attempt to collect pregnancy information on any male subject's female partner who becomes pregnant while the male subject is in this study. This applies only to male subjects who receive any study intervention.

After obtaining the necessary signed informed consent from the pregnant female partner directly, the Investigator will record pregnancy information on the appropriate form and submit it to the Sponsor within 24 hours of learning of the partner's pregnancy. The female partner will also be followed to determine the outcome of the pregnancy. Information on the status of the mother and child will be forwarded to the Sponsor. Generally, the follow-up will be no longer than 6 to 8 weeks following the estimated delivery date. Any termination of the pregnancy will be reported regardless of fetal status (presence or absence of anomalies) or indication for the procedure.

10.5 Appendix 5: Protocol Amendment History

The amendment history for Protocol AT01-001 is provided in Table 3.

Table 3: Protocol AT01-001: Amendment History

| Version | Version Date | Brief Description | |
|---------|-------------------|--|--|
| 2.0 | 08 March 2022 | Revisions from Version 1.1 include the following: | |
| | | Addition of slow IV bolus at 1 mL/5 seconds as a method of administration. | |
| | | Updated clinical experience to reflect final results from Study AMY1001. | |
| | | Minor administrative and editorial revisions. | |
| 1.1 | 07 October 2021 | Revisions from Version 1.0 include the following: | |
| | | • Addition of heparin/heparin analogs as a prohibited concomitant medication within 7 days of infusion of ¹²⁴ I-AT-01. | |
| | | Minor administrative and editorial revisions. | |
| 1.0 | 27 September 2021 | Original protocol; used for pre-submission activities. This version was not submitted to any health authorities or IRBs/ECs, nor was it implemented. | |

1 LIST OF ABBREVIATIONS

Table 1-1: List of Abbreviations

Abbreviation	Term
ADA	Anti-drug antibodies
AL	Amyloid light chain
ATC	Anatomical Therapeutic Chemical
ATTR	Amyloid transthyretin
ATTRv	Hereditary Amyloid transthyretin
ATTRwt	Wild type Amyloid transthyretin
BMI	Body mass index
BNP	Brain natriuretic peptide
CI	Confidence interval
CNR	Contrast to noise ratio
CRF	Case report form
CT	Computed tomography
dFLC	Difference in involved and uninvolved free light chains
eGFR	Estimated glomerular filtration rate
EOS	End of study
FLC	Free light chains
ICC	Intraclass Correlation Coefficient
ICF	Informed consent form
ICH	International Conference on Harmonisation
IES	Image evaluable set
IRR	Infusion-related reaction
IV	Intravenous
KI	Potassium iodide
MedDRA	Medical Dictionary for Regulatory Activities Terminology
PET	Positron emission tomography
SAE	Serious adverse event
SAP	Statistical Analysis Plan
SD	Standard deviation

Page 7 of 38

SGOT	Serum glutamic-oxaloacetic transaminase (replaced by AST)
SGPT	Serum glutamic-pyruvic transaminase (replaced by ALT)
SMQ	Standardized MedDRA Query
SNR	Signal to noise ratio
SOA	Schedule of activities
SUV	Standardized uptake value
TEAE	Treatment-emergent adverse event
UACR	Urine albumin-to-creatinine ratio
WBC	White blood count
WHO	World Health Organization

2 PURPOSE OF THE ANALYSES

The purpose of this statistical analysis plan (SAP) is to provide detailed information to aid in the implementation of the statistical analysis of the study data. It briefly summarizes the protocol, describes the analysis sets that will be analyzed, and describes the analyses to be performed. The details of the specific statistical methods that will be used are provided. Table, figure, and listing specifications are in separate documents. This analysis plan is meant to supplement the study protocol. If differences occur between analyses described in the SAP and the current protocol, those found in this SAP will assume primacy.

This SAP is written with due consideration of the recommendations outlined in the most recent International Conference on Harmonisation (ICH) E9 Guideline entitled Guidance for Industry: Statistical Principles for Clinical Trials and the most recent ICH E3 Guideline, entitled Guidance for Industry: Structure and Content of Clinical Study Reports and will be finalized prior to database lock.

3 PROTOCOL SUMMARY

3.1 Study Rationale

There currently are no approved imaging agents that specifically detect and quantify amyloid deposits in subjects.

As a positron emission tomography (PET)/X-ray computed tomography (CT) imaging agent that binds many forms of human and murine amyloid, ¹²⁴I-AT-01 may fulfill this unmet clinical need by enabling detection of amyloid in abdominothoracic organs or tissues of subjects with systemic amyloidosis. Thus, this study has been designed to assess the repeatability of organ-specific quantitation of radiotracer uptake following PET/CT imaging of ¹²⁴I-AT-01 in subjects with amyloid light chain (AL) or amyloid transthyretin (ATTR) systemic amyloidosis. This will help to determine whether ¹²⁴I-AT-01 can be used to monitor disease progression and treatment response in subjects with systemic amyloidosis.

3.2 Study Objectives

The primary study objective is to evaluate the repeatability of organ-specific quantitation of radiotracer uptake following PET/CT imaging of ¹²⁴I-AT-01 in subjects with AL or ATTR systemic amyloidosis.

The secondary study objective is to characterize the safety and tolerability of repeat doses of ¹²⁴I-AT-01 administered by intravenous (IV) infusion or slow IV bolus.

3.3 Study Design

This is a multicenter, open-label, single arm study in subjects with AL or ATTR systemic amyloidosis. ¹²⁴I-AT-01 is the only study intervention; neither reference therapy nor placebo will be administered.

This study consists of a screening period of up to 30 days; two, one-day treatment periods (Day 1 and Week 6); a safety follow-up 1-3 days after the second administration of 124 I-AT-01, and a final safety follow-up 28 ± 3 days after the second administration of 124 I-AT-01. Thus, the total subject duration is approximately 14 weeks. A study flow chart is provided in appendix 14.1 and a schedule of events is provided in appendix 14.2.

A formal sample size calculation is not provided for this study. The sample size of up to 20 subjects was estimated based on systematic literature review analysis sets.

3.4 Study Population

¹²⁴I-AT-01 is designed to selectively bind to amyloid; therefore, the objectives of this study can only be met by including subjects with documented systemic amyloidosis and known visceral organ amyloid deposits. Subjects with AL or ATTR systemic amyloidosis were selected for this study because these are the most common forms of systemic amyloidosis at the study sites.

Page 10 of 38

4 GENERAL ANALYSIS AND REPORTING CONVENTIONS

The following general analysis and reporting conventions will be used:

- Categorical variables will be summarized using counts (n) and percentages (%) and will be presented in the form n (%). If a count is 0, no percentage will be shown. To ensure completeness, summaries for categorical variables will include all categories, even if no subjects had a response in a particular category. Denominators will include subjects with non-missing data, unless otherwise specified. The number of subjects with missing data for categorical variables will be summarized without a percentage.
- Continuous variables will be summarized using mean, standard deviation (SD), minimum, maximum, median, and number of subjects. The mean, median, and confidence intervals (CI) will be rounded and reported to 1 more level of precision than the original observations, and the SD will be rounded and reported to 2 more levels of precision than the original observations. The minimum and maximum will be the same precision as the original data.
- Following SAS default rules, the median will be reported as the rounded average of the two middle numbers if the dataset contains even numbers.
- P-values, if any are provided, will be rounded and reported to 3 decimal places if greater than 0.001. If the rounded p-value is less than 0.001, '<0.001' will be reported. If the rounded p-value is >0.999, '>0.999' will be reported.
- Unless otherwise specified, the baseline value for all measures is the last non-missing value prior to the first dose, obtained on or before the date of the first dose of study drug. For measurements that occur on the date of the first dose of study drug with time collected, the measurement will be considered the baseline value if the measurement time is prior to the time of the first dose.
- No preliminary rounding will be performed; rounding will only occur after analysis. To round, consider digit to right of last significant digit: if < 5 then round down, if ≥ 5 then round up.
- All listings will be sorted in order of subject, parameter (when applicable), and time of assessment (e.g., visit, time, and/or event).
- Dates in listings will be displayed as yyyy-mm-dd (e.g., 2021-10-14).
- Age (in years) will be calculated as [(date of informed consent date of birth)] /365.25 and will be reported as the integer part of the derived age, with no rounding, in the analysis datasets, tables, and listings.
- All analyses will be performed using the SAS System version 9.4.

Page 11 of 38

5 ANALYSIS SETS

The analysis sets for the planned analyses are defined as follows:

• Enrolled Set

The Enrolled Set is defined as all subjects who signed the informed consent form (ICF) and met eligibility criteria.

• Safety Set

Version Date: 2022-12-16

The Safety Set is defined as all subjects who receive any amount of ¹²⁴I-AT-01. The Safety Set will be used for safety analyses.

• Image Evaluable Set

The Image Evaluable Set (IES) is defined as all subjects who undergo PET/CT scans on both Day 1 and 6 to 8 weeks after Day 1 and who have evaluable images at both time points. The IES will be used for analyses of repeatability.

Version: 2.0

6 STUDY SUBJECTS

6.1 Disposition of Subjects

The following disposition information will be summarized for all subjects who signed the ICF:

- The number of subjects screened
- The number of subjects who screen failed (subjects who fail screening once, are rescreened, and are treated in the study are counted as screen failures and as enrolled subjects. Subjects who fail screening twice are counted only once as screen failures.)
- The number of subjects who received any study treatment
- The number of subjects who received two doses of AT-01
- The number of subjects in each analysis set
- The number and percentage of subjects who completed the study
- The number and percentage of subjects who discontinued the study and the reason for premature study discontinuation
- The number and percentage of subjects who discontinued the study due to COVID-19
- The distribution of the number of days relative to first dose of study drug (i.e., date of discontinuation date of first dose + 1) for subjects who prematurely discontinue from the study

A data listing of subject disposition for all subjects who signed the ICF will also be provided.

6.2 Demographic and Other Baseline Characteristics

Subject demographics and other baseline characteristics will be summarized for the Safety Set.

The table will include age, sex, race, ethnicity, height, weight, body mass index (BMI), estimated glomerular filtration rate (eGFR), time since diagnosis of systemic amyloidosis, organ involvement, amyloid subtype, ATTRwt, mutation type for ATTRv subjects, free light chains (FLC) type for AL subjects, normal FLC ratio (kappa/lambda; between 0.26 and 1.65, inclusive for subjects with eGFR >= 30 mL/min/1.73m², between 0.37 to 3.17 for subjects with eGFR <30 mL/min/1.73m²), difference between involved and uninvolved serum free light chains (dFLC), NT-proBNP, BNP, and UACR.

If age is missing, age (years) will be calculated relative to the date of informed consent, as described in Section 4.

Years since diagnosis of systemic amyloidosis will be calculated as year of diagnosis date relative to the year of informed consent (i.e., year of informed consent – year of diagnosis).

eGFR will be calculated via the CKD-EPI equation and have a unit of mL/min/1.73m²:

Page 13 of 38

eGFR = 141 x min(SCr/ κ , 1)^{α} x max(SCr / κ , 1)^{-1.209} x 0.993^{Age} x 1.018 [if female] x 1.159 [if Black], where SCr (standardized serum creatinine) = mg/dL, κ = 0.7 (females) or 0.9 (males), α = -0.329 (females) or -0.411 (males).

Demographic and baseline characteristics will be presented in data listings for all enrolled subjects.

A listing of baseline disease characteristics will also be provided.

6.3 Medical, Surgical, and Procedural History

Medical history includes clinically significant diseases, organ or stem cell transplants, and reproductive status. Medical history will be coded using Medical Dictionary for Regulatory Activities Terminology (MedDRA) version 24.1 and will be summarized as counts and percentages for the Safety Set by system organ class and preferred term. A subject will be counted only once for each condition. A listing of medical history data will be provided.

A by-subject listing of surgical and procedural history will be provided.

6.4 Prior and Concomitant Medications

The prior and concomitant medications will be coded using the latest version of World Health Organization Drug Dictionary (WHO Drug), Global version (2021-SEP) to identify the drug class and preferred drug name.

Concomitant medications will include all medications that started on or after day of first dose of the study drug or that stopped on or after day of first dose of study drug, including medications that are classified as ongoing. Prior medications will include all medications that started and stopped prior to the day of first dose of the study drug. Any medication with a partially missing start date or stop date which allows the possibility that the medication is both prior and concomitant will be classified as both. Any medication with a completely missing stop date (i.e., day, month, and year are missing) will be classified as ongoing. For a medication with a completely missing start date, the medication will be classified as both a prior and concomitant medication unless the stop date is prior the date of first dose of study drug, in which case the medication will be classified as a prior medication.

The number and percentage of subjects using prior medications, and separately concomitant medications will be tabulated by Anatomical Therapeutic Chemical (ATC) level 3 term, and preferred drug name for all subjects in the Safety Set. A subject will be counted at most once within each ATC level 3 term, and preferred drug name combination. All percentages will use the number of subjects in the Safety Set as the denominator. The tabular summaries will be sorted by descending overall frequency by ATC level 3 term, and preferred drug name.

Prior and concomitant medication data will also be presented in a data listing for subjects in the Safety Set.

The above tabulations will be repeated for prior and concomitant medications reported on the amyloid medication case report form (CRF) for the treatment for systemic amyloidosis.

Page 14 of 38

7 STUDY OPERATIONS

7.1 Protocol Deviations

Protocol deviations will be summarized by severity (i.e., major or minor) and category and provided in a listing. Any exclusion of subjects from exploratory analysis populations, and how these exclusions impact data analysis, will be addressed in the clinical study report.

7.2 Measures of Treatment Compliance

Treatment compliance is summarized in section 9.2.

8 ENDPOINT EVALUATION

8.1 Overview of Efficacy Analysis Methods

8.1.1 Multicenter Studies

Study subjects will be enrolled from multiple study sites in the United States. For all analyses, study data will be analyzed and summarized as a whole, and no formal accommodation for site-to-site variation will be made. Site identifiers will be included in bysubject listings.

8.1.2 Assessment Time Windows

The following study visits are scheduled:

Table 8-1: Assessment Time Windows

Visit	Analysis Visit Number	Window	Target Day
Screening	0	Day -30 to Day 1	N/A
Visit 1/Day 1	1	Day 1	1
Visit 2 /Week 6	2	After Day 1 to Week 8	43
Safety Follow-up 1	3	1-3 days after second infusion	1 day after second infusion date
Safety Follow-up 2/EOS/ET	4	28 (25-31) days after second infusion	28 days after second infusion date

All scheduled visits including assessments performed outside the target window, will be included in summary tables, figures, and listings. Scheduled visit data will be presented according to the nominal CRF recorded visit. Early termination visit and unscheduled visit data will be mapped to scheduled visits using the windows in Table 8-1. Early termination visit and unscheduled visit data will be included in tables and figures if no scheduled visit data is available for the nominal CRF recorded visit. If more than one unscheduled assessment (early termination or unscheduled) is performed within an analysis window for a visit without a nominal CRF record, the assessment performed closest to the target day will be used, if there is a tie, the earlier assessment will be used.

For clinical laboratory evaluation tables, early termination visits and unscheduled safety data will be mapped to scheduled visits using analysis windows. For all other safety tables and figures, early termination visits and unscheduled safety data will not be mapped to scheduled visits using analysis windows. All data, scheduled and unscheduled, will be included in listings.

Page 16 of 38

Version Date: 2022-12-16 Version: 2.0

Document Control No.: TMP-SA-008-01 Template Effective Date: 23 Mar 2021

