- d. Subjects must remain semi-recumbent for at least 5 minutes prior to blood pressure measurements. Blood pressure and heart rate will be measured within an hour prior to dosing and 5-10 minutes after administration of ¹²⁴I-AT-01.
- e. Serum pregnancy test, as indicated in Section 10.2, will be obtained in all women of childbearing potential.
- f. Serum pregnancy and all other laboratory samples must be drawn within 7 days prior to administration of ¹²⁴I-AT-01 in all WOCBP. The results of the pregnancy test must be available and be negative prior to ¹²⁴I-AT-01 administration in all WOCBP.
- g. Adverse events will be monitored from Screening through the EOS Visit. For Safety Follow-up 1 and 2, adverse events and concomitant medications can be obtained by phone call.
- h. Clinical laboratory tests and biomarker analysis, as described in Section 10.2. Baseline sample will be collected within 30 days prior to the first administration of ¹²⁴I-AT-01; second sample within 7 days prior to the second administration of ¹²⁴I-AT-01; third sample at Safety Follow-up 1 after the second administration of ¹²⁴I-AT-01.
- i. Urine and blood may be collected locally by visiting nurse/phlebotomist. An additional serum ADA sample will be obtained at Screening for subjects who provided consent for the extra ADA sample.
- j. Safety follow-ups for concomitant medications and adverse events will be done via telephone call for all subjects. Both Safety Follow-up 1 and Safety Follow-up 2 activities will be conducted for subjects who discontinue for IRRs at either the first or second administration of ¹²⁴I-AT-01.
- k. Blood draw for ADA should be obtained if ET is ≥4 weeks after first administration of ¹²⁴I-AT-01.
- l. Early Termination activities do not apply to subjects discontinued for IRRs. Please follow Safety Follow-up 1 and Safety Follow-up 2 activities for subjects experiencing IRR with either the first or second administration of ¹²⁴I-AT-01.

- 15 -

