4.1.3 Administration Period

Administration of ¹²⁴I-AT-01 and the associated study procedures occur at the Day 1 and Week 6 (+ 2 week) visits. Administration of ¹²⁴I-AT-01 and the associated study procedures are described in Section 4.1.3.1.

4.1.3.1 Administration of Study Intervention(s) and Associated Procedures Day 1 and Week 6 (+ 2 week) Visits

The schedule for administration of ¹²⁴I-AT-01 is provided in the SoA (Section 1.3). Administration of ¹²⁴I-AT-01 occurs at the Day 1 and Week 6 to Week 8 visits, as follows:

Prior to Administration of ¹²⁴I-AT-01

- 1) Clinical laboratory tests and biomarker analysis (including serum pregnancy test in WOCBP) will be obtained within 7 days prior to the second administration of ¹²⁴I-AT-01, as described in the SoA (Section 1.3). The results of the pregnancy test must be available and be negative prior to ¹²⁴I-AT-01 administration in all WOCBP.
- 2) Instruct subject to take oral KI daily for 3 days, as described in Section 4.1.2.
- 3) Record concomitant medications and monitor and record AEs throughout the study visit.

Administration of ¹²⁴I-AT-01

4) Subjects enrolled under protocol Version 2.0 will receive a single dose of 1 mCi (± 10%) 124I-AT-01 by slow IV bolus at a rate of 1 mL/ 5 seconds. During 124I-AT-01 administration, monitor subjects for infusion-related reactions (IRRs), as described in Section 7.1.1. For all subjects, 124I-AT-01 will be administered by the same route (IV infusion over 2-5 minutes or slow IV bolus at 1 mL/5 seconds) at the Week 6 visit as on the Day 1 visit.

After Completion of Administration of ¹²⁴I-AT-01

- 5) Blood pressure and heart rate will be measured 5-10 minutes after administration of ¹²⁴I-AT-01.
- 6) Subjects will undergo a PET/CT scan 5 hours (± 30 minutes) after the start of administration of ¹²⁴I-AT-01 to quantify ¹²⁴I-AT-01 uptake in organs. ¹²⁴I-AT-01 whole-body scans will be acquired by study-designated PET/CT scanners, as described in Section 8.1.4.
 - Subjects will be discontinued if amyloid deposits are not identified in the Day 1 PET/CT scan in at least one of the following organs: heart, liver, spleen or kidney (i.e., they will not receive a second administration of ¹²⁴I-AT-01 or undergo a second scan) and will undergo early termination (ET) activities, as provided in the SoA (Section 1.3) and as described in Section 4.1.5.
- 7) Any adverse events will be recorded; patient can be discharged after completing the scan and deemed stable by study staff.

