6.6 Access to Study Intervention After End of Study

Administration of ¹²⁴I-AT-01 under this protocol will be completed at Visit 2 (Week 6 to Week 8). No further treatment with ¹²⁴I-AT-01 will occur under this protocol, and ¹²⁴I-AT-01 will not be made available to subjects by the Sponsor after completion of the study.

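### The SAP's Visit 2 laboratory window opens on Day 2 and is not capped at the second dose, so in a subject with no scheduled Visit 2 lab a stray unscheduled lab can be tabulated as Week 6

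*SAP*

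**What the plan says.** SAP section 8.1.2, Table 8-1, gives Visit 2/Week 6 the window "After Day 1 to Week 8" with target Day 43. Safety Follow-up 1 has the window "1-3 days after second infusion" and the target "1 day after second infusion date".

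The text under the table says: "Early termination visit and unscheduled visit data will be mapped to scheduled visits using the windows in Table 8-1". It then sets these limits:

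- Scheduled visits keep the visit recorded on the CRF.
- Unscheduled or early termination results enter tables only where that visit has no scheduled data.
- If several such results fall in one window, the one nearest the target day is used, and the earlier one if tied.
- Among safety tables, window mapping is used only for clinical laboratory tables. SAP section 9.5 repeats this for unscheduled visits.

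The protocol's timing is narrower. Section 4.1.3.1 states: "Administration of ¹²⁴I-AT-01 occurs at the Day 1 and Week 6 to Week 8 visits". Footnote h of the Schedule of Activities (section 1.3) places the Visit 2 lab as follows: "second sample within 7 days prior to the second administration of ¹²⁴I-AT-01". Protocol section 8.2.2 allows unscheduled safety labs when the investigator considers them necessary. Change from baseline in laboratory values at Visit 2 and Safety Follow-up 1 is a secondary endpoint (protocol section 3.0, SAP section 9). SAP section 2 gives the SAP precedence where its analyses differ from the protocol's.

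**The concern.** The Visit 2 lab is meant to be a pre-dose sample about six weeks after the first administration. The SAP window admits any laboratory result from the day after that administration, so it can label an early post-dose-1 value as Week 6.

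The subjects exposed to this are foreseeable. Those with no amyloid on the Day 1 scan, those stopped for certain infusion-related reactions, and those given heparin before the second visit do not reach dose 2, yet all remain in the Safety Set on which laboratory tables are built. The nearest-to-target rule gives no protection when there is only one unscheduled result.

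The second gap is at the other end. The window does not close at dose 2, and the SAP has no rule for a result that fits both Visit 2 and Safety Follow-up 1. The tie rule chooses between results in one window, not between windows.

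At stake is the reading of a named secondary safety endpoint in a small study. A laboratory change that arose days after dose 1 could be shown as a six-week change, or a value taken after dose 2 as a pre-dose one.

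**Working it through.** **Inputs**

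- Visit 2 window and target Day 43: SAP Table 8-1.
- Safety Follow-up 1 window, dose 2 plus 1 to 3 days: SAP Table 8-1.
- Dose 2 at Week 6 to Week 8: protocol section 4.1.3.1.
- Visit 2 lab within 7 days before dose 2: protocol section 1.3, footnote h.

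**Day convention.** With Day 1 as the first dose, Week 6 = 6 × 7 + 1 = Day 43. This reproduces the SAP's target day. By the same convention Week 8 = 8 × 7 + 1 = Day 57.

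**Length of the windows**

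- SAP Visit 2 window, Days 2 to 57: 57 − 2 + 1 = 56 days.
- Permitted dose-2 days, Days 43 to 57: 57 − 43 + 1 = 15 days.
- Earliest permitted Visit 2 lab: 43 − 7 = Day 36.
- Window days before any permitted lab, Days 2 to 35: 35 − 2 + 1 = 34, and 34/56 = 61%.

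**Overlap with Safety Follow-up 1.** If dose 2 is on day d, that window is d + 1 to d + 3. It lies wholly inside the Visit 2 window when d + 3 ≤ 57, so d ≤ 54.

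| Dose-2 day | Number of days | Overlap |
|---|---|---|
| 43 to 54 | 12 | whole |
| 55 and 56 | 2 | partial |
| 57 | 1 | none |

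**Sensitivity to the convention.** With Week 6 as Day 42 and Week 8 as Day 56, the SAP window is 55 days and the earliest lab is Day 35. The unjustified span is Days 2 to 34, which is 33 of 55 days (60%). The overlap counts remain 12, 2 and 1.

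**Two cases traced through the SAP's rules**

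1. A subject is stopped after the Day 1 scan and has one unscheduled lab on Day 3. There is no scheduled Visit 2 lab and Day 3 lies in the Visit 2 window. There is no second infusion date to define any later window. The Day 3 value is tabulated as Week 6.
2. A subject receives dose 2 on Day 43 and has an unscheduled lab on Day 44. It is 1 day from the Visit 2 target and 0 days from the Safety Follow-up 1 target, and it fits both windows. It can enter the Visit 2 row only if the required pre-dose lab is missing.

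**Would simpler windows do?** A bare Day 43 to 57 window would lose valid pre-dose labs from Days 36 to 42 and would still overlap Safety Follow-up 1. A fixed Day 36 start for everyone does not match the protocol either: with dose 2 on Day 57, a Day 36 sample is 57 − 36 = 21 days before the dose.

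**The case against.** The best defence is that this is only a fallback rule. A scheduled Visit 2 lab always stands, and the scheduled Safety Follow-up 1 draw stays under its own visit. That is correct, and it defeats several stronger readings that a reader might infer:

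- **That unscheduled values displace real Week 6 values.** They cannot; they enter only where no scheduled Visit 2 value exists.
- **That post-dose values readily enter Visit 2.** This needs both a missed protocol-required pre-dose lab and an unscheduled post-dose draw.
- **That early termination feeds labs into Week 6.** The Schedule of Activities has no safety lab at early termination. Its only sample there is for anti-drug antibodies, whose analysis the SAP places outside its scope.
- **That every reaction at dose 1 produces a false Week 6 value.** Subjects discontinued for such a reaction have Safety Follow-up 1 activities, including a lab reported under its nominal visit. Only an additional unscheduled draw, or one recorded as unscheduled, is exposed.
- **That everything before Day 43 is wrong (41 of 56 days, 73%).** Labs from Day 36 are permitted, so the span is 34 days. Either figure is a share of calendar days, not of records or subjects.
- **That the mapped values are the abnormal ones.** The protocol says only that unscheduled labs may be done when judged necessary.
- **That each visit has at most 20 subjects.** Protocol section 5.5 replaces subjects who lack a second dose, so the Safety Set can exceed 20.

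It is also true that the laboratory summaries are descriptive, that all results are listed, and that the Image Evaluable Set has its own 6-to-8-week scan requirement. What survives is the rule itself: where it does operate, neither document justifies a Day 2 start or an open end at dose 2.

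**Conclusion.** The Visit 2 laboratory window is wrong as written, with limited effect. It covers 56 days, of which 34 (61%) precede any sample the protocol permits for that visit. It also overlaps Safety Follow-up 1, wholly or partly, for 14 of the 15 permitted dose-2 days. In a subject with no scheduled Visit 2 lab, a lone unscheduled result soon after dose 1 would be reported as the Week 6 change from baseline.

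The number of affected records cannot be derived from the documents, which do not say how many unscheduled labs to expect; it is probably small. With around 20 subjects, one misplaced value carries about 1/20 of the weight in a visit mean, which can be visible in a descriptive table. The primary repeatability analysis is not touched. This is a low-priority correction, worth making because it is cheap and the endpoint is named.

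The conclusion assumes that Day 1 is the first dose and that Week 6 is Day 43, as the SAP's target implies. The alternative convention changes the share only from 61% to 60%.

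**What to change.** In SAP section 8.1.2, for laboratory mapping only:

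1. For subjects who receive dose 2, define Visit 2 as the 7 days before the second administration, with the sample taken before that administration.
2. For subjects who do not receive dose 2, define it as Day 36 to Day 57.
3. State that no sample taken after dose 2 is mapped to Visit 2. This removes the overlap with Safety Follow-up 1.
4. State that unscheduled labs taken after dose 1 but before that window are not tabulated as Week 6. Keep them in the listings and in the assessment of clinically significant changes (Appendix 14.3).

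A separate table row for labs after dose 1 is optional. It would mean changing the laboratory table shells; without it, the change is one table entry and a few sentences. No data are discarded. The downside is that a few subjects will show a missing Visit 2 lab.
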